Study Period II: Qualified patients will enter Study Period II (prospective baseline) to determine their eligibility for the study and to establish baseline data for comparison of endpoints during the double-blind treatment phase. Beginning at Visit 2, patients will log in daily to the electronic patient-reported outcomes (ePRO) system to answer questions about the occurrence of headaches, headache duration, headache features, severity of headache, and whether any acute headache medication was taken. Also beginning at Visit 2, patients will record the name, dose, and date of any acute headache medication on a headache medication log which will be returned to site staff at each study visit. At the end of the prospective baseline period, sites will be notified whether their patients met criteria and are eligible to be randomized at Visit 3.

To avoid biased reporting, patients must not be told the number of migraine or headache days on which study qualification is based.

Study Period III: At the start of the 3-month double-blind treatment phase (Visit 3), patients meeting all eligibility requirements will be randomized in a 1:1 ratio to receive 120 mg/month galcanezumab (with an initial 240-mg loading dose) or placebo. At Visit 3, if available and where local regulations and ethical review boards (ERBs) allow, patients will also watch a training video designed to address patient expectations with regard to participation in a placebo-controlled trial and the difference between medical treatment and research. To preserve blinding, patients in both treatment groups will receive 2 injections of investigational product at the first dosing visit (2 galcanezumab injections of 120 mg or 2 placebo injections) and then 1 injection of investigational product (120-mg galcanezumab or placebo) for the next 2 dosing visits.

The patient will be considered enrolled in the study when randomization occurs. During this phase, study procedures at dosing visits must always occur prior to the patient receiving their assigned treatment.

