Objectives	Endpoints		
Secondary Objectives (continued)			
To compare galcanezumab with placebo with respect to changes in disability and quality of life	 Changes from baseline to Month 3 on the following measures: Migraine Disability Assessment (MIDAS) total score and individual items MSQ v2.1 total score, and Role Function-Preventive and Emotional Function domain scores Health Care Resource Utilization (HCRU) and Employment Status European Quality of Life Questionnaire 5-Dimensions 5-Levels (EQ-5D-5L) Migraine Interictal Burden Scale (MIBS-4) Work Productivity and Activity Impairment Questionnaire (WPAI) 		
To compare galcanezumab with placebo with respect to change in patient global impression of the severity of migraine	 Mean change from baseline in the Patient Global Impression of Severity (PGI-S) score at Month 3 		
To compare galcanezumab with placebo with respect to changes in migraine attacks (episodic migraine subpopulation only)	The overall mean change from baseline in the number of monthly migraine attacks during the 3-month double- blind treatment phase in patients with episodic migraine		
To compare galcanezumab with placebo with respect to 30% response rate (chronic migraine subpopulation only)	• The percentage of chronic migraine patients with ≥30% reduction from baseline in monthly migraine headache days during the 3-month double-blind treatment phase		
To compare galcanezumab with placebo with respect to safety and tolerability ^b	 Analysis of: treatment-emergent adverse events (TEAEs) serious adverse events (SAEs) discontinuation due to AEs discontinuation rates vital signs and weight electrocardiograms (ECGs) laboratory measures 		
To assess changes in efficacy, safety, and functional outcomes during Study Period IV (open-label treatment)	 In Study Period IV: Mean changes in all continuous measures of efficacy, safety, and functional outcomes that are also assessed in the double-blind phase Among patients previously treated with galcanezumab who meet 50% response criteria at Month 3 in the double-blind treatment phase, the proportion of patients who demonstrate 50% response for all 3 months in the open-label treatment phase 		

[figure not shown]
(Table CGAW.4.1. continued)

Objectives	Endpoints
Tertiary Objectives Note: All tertiary objectives will be tested in both the total population (episodic and chronic migraine) and the episodic migraine subpopulation.	

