5.4. Endpoints

5.4.1. Efficacy Endpoints

Migraine and headache endpoints are defined in Table CGAW.5.1. Each month is defined as a 30-day period with migraine or headache measures normalized from the visit intervals.

 Table CGAW.5.1.
 Migraine and Headache Endpoint Definitions

Diagnosis	Definition/Criteria		
Migraine headache	A headache, with or without aura, of ≥30 minutes duration with both of the		
	following required features (A and B):		
	A. At least 2 of the following headache characteristics:		
	Unilateral location		
	Pulsating quality		
	Moderate or severe pain intensity		
	 Aggravation by or causing avoidance of routine physical activity 		
	AND		
	B. During headache at least one of the following:		
	Nausea and/or vomiting		
	Photophobia and phonophobia		
	(Definition adapted from the standard IHS ICHD-3 definition)		
Probable migraine headache	A headache of ≥30 minutes duration, with or without aura, but missing one of the		
	migraine features in the IHS ICHD-3 definition (ICHD-3 2013). To be exact, it		
	meets either at least two A criteria and zero B criteria, or one A criteria and at		
	least one B criteria.		
Migraine headache day	A calendar day on which a migraine headache or probable migraine headache		
(primary objective)	occurs.		
ICHD migraine headache day	A calendar day on which a migraine headache occurs.		
Migraine headache attack	Beginning on any day a migraine headache or probable migraine headache is		
	recorded and ends when a migraine-free day occurs.		
Non-migraine headache	All headaches of ≥30 minutes duration not fulfilling the definition of migraine or		
	probable migraine.		
Non-migraine headache day	A calendar day on which a non-migraine headache occurs.		
Headache day	A calendar day on which any type of headache occurs (including migraine,		
	probable migraine, and non-migraine headache).		

Abbreviations: ICHD = International Classification of Headache Disorders; IHS = International Headache Society.

Headache information will be collected via an electronic patient-reported outcomes (ePRO) diary. Patients will need to enter ePRO diary data daily beginning from Visit 2 and continuing until Visit 9.

Information recorded in the ePRO diary, the possible responses and the assignment to the type of headache is presented in Table CGAW.5.2.

Table CGAW.5.2. ePRO Diary Questions, Responses, and Assignment to Headache Type

QUESTION	RESPONSES	HEADACHE ASSIGNMENT

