• Number of migraine attacks is calculated as the number of sets of consecutive migraine headache days separated by at least 1 migraine headache-free day in a 30-day period. For example, a migraine headache day starting on 5JAN and ending on 6JAN will result in a migraine headache free day on 7JAN (assuming that it is not a migraine headache day on 7JAN). This will count as 1 migraine attack that started on 5JAN and ended on 6JAN. For a migraine attack that begins in 1 30-day period but ends in another, only 1 migraine attack will be counted in the first of the 2 periods. For example, in the case of 7 days of consecutive migraine headache days with 3 days in baseline period and 4 days in Month 1, only 1 migraine attack will be counted in the baseline period; the 4 days of migraine headache days in Month 1 will not be counted as migraine attack in Month 1.

This measure (number of migraine attacks) is needed for the episodic migraine subpopulation only.

Additional secondary and exploratory efficacy measures will be derived as follows:

• Percent change from baseline in the number of migraine headache days will be calculated for any postbaseline 30-day period as:

$$-1*\frac{100\times(\text{\# of MHD in Month Y}-\text{\# of MHD in baseline period})}{\text{\# of MHD in baseline period}}$$

- An X% responder is defined as Yes, if any patient who has a ≥X% reduction in the total number of migraine headache days in a 30-day period relative to baseline period, as No if otherwise. Therefore, if the percent change from baseline in the number of migraine headache days is ≥X%, the patient will be counted as an X% responder. In other words, if the response rate defined above in a month is ≥X%, then the patient will be an X% responder in that month. Indicators of X% responders will be derived for X=30, 50, 75, and 100.
- Proportion of patients who continue to demonstrate >=50% response for all 3 months in the open-label treatment period. This analysis will include patients previously treated with galcanezumab who met 50% response criteria at Month 3 in the double-blind treatment phase (SP III) and entered the open-label treatment phase (SP IV). If a patient has missing data due to either early discontinuation or diary non-compliance such that response cannot be calculated for each of the 3 months in the open-label treatment period, then the patient will be considered a non-responder.

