5.5.1.2. Handling of Dropouts or Missing Data

Two statistical approaches to handling missing data will be used as appropriate: repeated measures analyses and ANCOVA/ANOVA model using change from baseline to LOCF endpoint.

For the repeated measures analyses, the model parameters are simultaneously estimated using restricted likelihood estimation incorporating all of the observed data. Estimates have been shown to be unbiased when data are missing at random.

Please refer to Section 5.4.1 for approach to handling missing diary data for derivation of migraine headache days and other efficacy measures (with the exception of migraine attacks) derived from ePRO data per 30-day period.

Approaches to handling missing diary data for the derivation of migraine attack

For the derivation of the number of monthly migraine attacks, the LOCF method will be used to impute the missing ePRO diary days. If the patient was migraine headache-free on the day before the missing ePRO diary day, this would be carried forward as no migraine headache day until the actual next non-missing diary day. On the other hand, if the day before the missing ePRO diary day is a migraine headache day, then it would be carried forward as migraine headache day until the next non-missing diary day. The imputation will be carried out for all the missing diary days between the first non-missing to the last day.

If the diary compliance rate for a monthly interval is \leq 50%, the number of monthly migraine attacks during that month will be considered missing. Please refer to Section 5.5.7 for diary compliance rate calculation.

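### Baseline migraine attacks appear to include a run already under way on the first diary day, while treatment months count onsets only, so the within-arm fall in attacks is slightly overstated

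*SAP*

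**What the plan says.** SAP 5.4.1 defines the number of migraine attacks as "the number of sets of consecutive migraine headache days separated by at least 1 migraine headache-free day in a 30-day period". When an attack starts in one period and finishes in the next, "only 1 migraine attack will be counted in the first of the 2 periods". The worked example is a 7-day run with 3 days in baseline and 4 in Month 1. It counts once, in baseline, and "the 4 days of migraine headache days in Month 1 will not be counted as migraine attack in Month 1".

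Three other provisions determine what happens at the start of baseline:

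- SAP Table CGAW.5.1 describes an attack as "Beginning on any day a migraine headache or probable migraine headache is" recorded, lasting until the first migraine-free day.
- Protocol 5.1 starts the diary with the baseline period: "Beginning at Visit 2, patients will log in daily to the electronic patient-reported outcomes (ePRO) system". SAP 5.4.1 agrees: "Patients will need to enter ePRO diary data daily beginning from Visit 2 and continuing until Visit 9".
- SAP 5.5.1.2 fills missing days for the attack count by carrying the last diary day forward: "The imputation will be carried out for all the missing diary days between the first non-missing to the last day". The fill cannot reach back before the first entry.

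The endpoint, in SAP Table CGAW.4.1, is "The overall mean change from baseline in the number of monthly migraine attacks during the 3-month" double-blind phase, in patients with episodic migraine. SAP Table CGAW.5.5 has it analysed by MMRM for SP III and for SP III/IV.

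**The concern.** A change from baseline is meaningful only if both counts follow the same rule. Months 1 to 6 each have a preceding diary period, so a run in progress on their first day belongs to the month before and they count onsets alone. Baseline has nothing before it. A run in progress on its first diary day has no earlier period to go to and, read literally, opens an attack. Baseline then holds onsets plus any carried-in run, and a count of onsets alone is compared with it. A patient whose disease does not change would, on average, show a fall.

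At stake are the reported mean changes within each arm. These matter most in the open-label phase, where one objective is to describe mean changes in the continuous efficacy measures and there is no concurrent placebo group.

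**Working it through.** **The plan's own example.** Count a migraine day as an attack when the day before it, taken from the previous period where there is one, is not a migraine day. For the 3 + 4 day run this gives 1 in baseline and 0 in Month 1, as the SAP states.

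**Inputs**

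- m, migraine headache days per 30 days: 4 to 14 in the episodic definition (SAP Table CGAW.4.1, footnote a).
- L, baseline length: 30 to 40 days (Protocol Section 2, Schedule of Activities, footnote a).
- Scaling of counts to 30 days: SAP 5.4.1.
- d, mean attack length in calendar days: not in the documents. The values below are assumptions.

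**Formula.** Take a stationary two-state diary (migraine or no migraine on each day). The first diary day is a migraine day with probability m/30. Given that, it continues a run from the day before with probability 1 - 1/d. Such a run adds one attack to baseline and none to a later month. After scaling to 30 days:

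spurious change = -(m/30)(1 - 1/d)(30/L)

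True onsets per 30 days are m/d, so the bias as a share of true attacks is (d - 1)/L.

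| m | d | L = 30 | share at L = 30 | L = 40 |
|---|---|---|---|---|
| 6 | 1.3 | -0.20 x 0.231 = -0.046 | 0.3/30 = 1.0% | -0.035 |
| 9 | 1.6 | -0.30 x 0.375 = -0.113 | 0.6/30 = 2.0% | -0.084 |
| 12 | 2.0 | -0.40 x 0.500 = -0.200 | 1.0/30 = 3.3% | -0.150 |
| 12 | 2.5 | -0.40 x 0.600 = -0.240 | 1.5/30 = 5.0% | -0.180 |

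The 40-day column is 30/40 = 0.75 of the 30-day column, so it is exactly one quarter smaller in every row.

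**Simulation check.** With 300,000 diaries per setting and no treatment effect, the 30-day changes were -0.05, -0.12, -0.20 and -0.24. These agree with the formula within rounding and simulation error. A wider grid (m = 4 to 14, d = 1.25 to 3, L = 30 to 40) gave about -0.02 to -0.31 attacks per month, or 0.6% to 6.7% of the attack rate.

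**Between-arm check.** This used m = 9, d = 1.5 and L = 30, with assumed cuts in the daily onset probability of 10% on placebo and 35% on galcanezumab.

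| | SAP rule | Onsets only | Gap |
|---|---|---|---|
| Placebo change | -0.530 | -0.430 | -0.100 |
| Galcanezumab change | -1.750 | -1.651 | -0.099 |
| Difference | -1.219 | -1.220 | about 0 |

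The gap in each arm equals the formula value of 0.30 x (1 - 1/1.5) = 0.100, and it cancels in the contrast.

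**The case against.** The endpoint exists to compare galcanezumab with placebo, and SAP 5.5.10.3 estimates that comparison as the MMRM treatment main effect. The extra baseline run arises before randomisation, is equal in expectation in both arms, and cancels. This stands in full. A reader might infer that the treatment comparison is biased. The documents do not support that, because the same counting rule applies to both arms.

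The SAP never says how a run present on the first diary day is handled. This also stands. That it counts at baseline is inferred from the attack definition, the Visit 2 diary start, the forward-only fill and the absence of an exception. A reader might take it as a stated rule, but it is not one. If the programming already does something else, the SAP should say so.

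A reader might also want the artefact expressed as a share of the true fall, particularly on placebo. The documents give no expected within-arm change in attacks, so any such percentage would rest on an invented denominator.

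Finally, assigning a boundary attack to the earlier period is a sensible convention that prevents double counting, the endpoint is outside the gated sequence, and within-arm changes already contain placebo response and selection on baseline frequency. All true, and these points limit the importance. They do not make the two subtracted counts comparable, and the open-label mean changes have no control difference in which the artefact could cancel.

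**Conclusion.** The point holds as a small inconsistency in how one other secondary endpoint is derived. Followed as written, the SAP counts onsets plus a carried-in run at baseline and onsets only afterwards, which makes the within-arm mean change in monthly attacks slightly too favourable in both arms, in SP III and SP III/IV. The direction needs only that some attacks last more than one calendar day.

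The size, about -0.05 to -0.24 attacks per month (1-5% of the baseline count) for a 30-day baseline, rests on assumed attack lengths of 1.3 to 2.5 days, on 6 to 12 migraine days per 30 days, and on a stationary diary model. For a single patient it is at most one attack. The primary endpoint and the gated key secondary endpoints do not use the attack count. This is a worthwhile clarification and does not threaten the trial's conclusions.

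**What to change.** In SAP 5.4.1, define the count as onsets in every period: a migraine headache day that follows a migraine-free day, after the planned LOCF fill. For baseline, add that a run already present on the first diary day is not counted and that the count is scaled by 30/(baseline days - 1), because the first day can no longer contribute an onset.

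In simulation with no true change this brought the spurious change to between -0.004 and +0.001 in the eight settings run.

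The cost is one sentence or so in the SAP and one programming condition, with no new data and no effect on other endpoints. Genuine onsets on the first diary day are dropped too, and the scaling restores them only on average, so the baseline count becomes slightly more variable (SD about 1-2% larger). The reported mean reductions become slightly smaller.

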5.4.2. Other Efficacy Measures

5.4.2.1. Patient Global Impression

The Patient Global Impression of Severity (PGI-S) will be collected at baseline (Visit 3), the end of the double-blind treatment phase (Visit 6), and the end of the open-label treatment phase (Visit 9). In this single-item scale, patients rate the severity of their migraine condition on a scale ranging from "not at all ill" (coded as 1) to "extremely ill" (coded as 7).

Change from baseline in PGI-S scores will be summarized and analyzed.

5.4.3. Health Outcome Questionnaires

The following health outcome questionnaires are collected using patient direct data entry on an electronic device which does not allow patients to skip items. Patients either complete each scale in its entirety or not at all. Therefore, no imputation for missing values is necessary for these scales.

5.4.3.1. Migraine Specific Quality of Life (MSQ) v2.1

Migraine Specific Quality of Life (MSQ) v2.1 consists of 14 questions. The questions measure the impact of migraine on health-related quality of life across 3 domains: 1) Role Function-Restrictive (7 questions), examines the degree to which performance of daily activities is limited by migraine; 2) Role Function-Preventive (4 questions), examines the degree to which performance of daily activities is prevented by migraine; 3) Emotional Function (3 questions), examines feelings of frustration and helplessness due to migraine.

Precoded item values and final item values for MSQ item responses are shown in Table CGAW.5.3. All item values range from 1 to 6. Final item values will be used for analysis with higher scores reflecting better quality of life.

Table CGAW.5.3. Item Values for Migraine Specific Quality of Life (MSQ) Item Responses

Response Categories	Precoded Item Value	Final Item Value
None of the time	1	6
A little bit of the time	2	5
Some of the time	3	4
A good bit of the time	4	3
Most of the time	5	2
All of the time	6	1

Questions 1 to 7 of the questionnaire will be grouped together as Role Function-Restrictive domain, questions 8 to 11 as Role Function-Preventive domain and questions 12 to 14 as the Emotional Function domain.

The raw score of each domain will be calculated as the sum of the raw scores of each question in that domain. The total score will be calculated as the sum of Role Function-Restrictive, Role Function-Preventive, and Emotional Function domain scores.

The raw scores of each domain and the total score will be transformed to a 0 to 100 scale using the following formulae:

• Role Function-Restrictive (range of 7 to 42):

$$\frac{(\text{raw score} - 7) \times 100}{35}$$

• Role Function-Preventive (range of 4 to 24):

$$\frac{(\text{raw score} - 4)x100}{20}$$

• Emotional Function (range of 3 to 18):

$$\frac{(\text{raw score} - 3)x100}{15}$$

• Total Score (range of 14 to 84):

$$\frac{(\text{raw total score} - 14) \times 100}{70}$$

The transformed total score and domain scores will be analyzed.

5.4.3.2. MIDAS (Migraine Disability Assessment)

The Migraine Disability Assessment (MIDAS) is a patient-rated scale which was designed to quantify headache-related disability over a 3-month period. This instrument consists of 5 items that reflect the number of days reported as missed, or with reduced productivity at work or home and social events. Each question is answered as the number of days during the past 3 months of assessment, ranging from 0 to 90, with the total score being the summation of the 5 numeric responses. A higher value is indicative of more disability. This instrument is considered highly reliable and valid, and is correlated with clinical judgment regarding the need for medical care (Stewart et al. 1999, 2001). For clinical interpretability, 4 categorical grades were developed based on the total score: Grade I (0 to 5) is for little or no disability, Grade II (6 to 10) is for mild disability, Grade III (11 to 20) is for moderate disability, and Grade IV (21+) is for severe disability. The severe disability category has subsequently been subdivided into Grade IV-A (severe [21 to 40]) and Grade IV-B (very severe [41 to 270]) because a high proportion of patients with chronic migraine are in Grade IV (Blumenfeld et al. 2011).

MIDAS consists of 5 questions (Q1-Q5) and 2 additional questions (A and B). The questionnaire measures the impact that migraine headaches have on migraineurs' life, including days of work or school missed, days with productivity at work or school reduced to half or more, days with household work missed, days with productivity in household work reduced to half or more, and days missed family / social / leisure activities. Each question is answered as a number of days during the past 3 months of assessment, ranging from 0 to 90. The answers to all 5 questions will be added up to a total MIDAS score.

The total MIDAS score and item scores will be analyzed.

